9.2 Populations for Analyses

Efficacy will be evaluated on the basis of the modified intent-to-treat (mITT) analysis set. A supportive analysis will also be conducted on the per-protocol (PP) analysis set.

Modified Intent-to-Treat Population (mITT): This population will include all subjects who received at least one dose of the study product. All subjects will be analyzed according to the treatment group to which they were randomized. The mITT population will be used as the primary analysis population for efficacy.

The Per-Protocol Population (PP): This population will include all subjects who were randomized, who received at least one dose of study product, with no major protocol deviations, and who provided evaluable data for the primary endpoint. All subjects will be analyzed according to the treatment group that they actually received.

The Safety Population (SAF): This population will include all subjects who received at least one dose of the study product. All subjects will be analyzed according to the treatment group that they actually received.

The PK Population: This population will include all subjects who received at least one dose of ASN002 and have plasma concentration data.

The PD Population: This population will include all subjects who have at least one assessments of PD parameters

9.3 Statistical Analyses

9.3.1 General Approach

Continuous variables will be summarized in tables and will include the number of subjects, mean, standard deviation (SD), median, minimum, and maximum. Categorical variables will be presented in tables as frequencies and percentages.

The primary efficacy analysis will be done using the mITT population and the PP population will be used as supportive analysis. All efficacy analyses will be performed using Mixed Model Repeated Measures (MMRM) analyses as primary analyses to take care of missing observations.

Additional details regarding the efficacy and safety variable definitions, analyses strategy, control of the overall type 1 error, statistical justification, and techniques for handling missing values (e.g. for subjects who started prohibited medications) will be detailed in a SAP that will be prepared before the database is locked and any analyses are undertaken.

9.3.2 Efficacy Analyses

The primary efficacy endpoint will be analyzed using a repeated measures analysis of covariance on percent change-from-baseline variable to compare the time profile between treatments where

the visit will be the time factor (up to Week 16); and the stratification factor PGA score, treatment group, and interaction term for treatment-by-visit will be the fixed effects and the baseline value will be the covariate. An unstructured variance-covariance matrix will be used. Additional interaction terms will also be included in supportive statistical models and will be detailed in the SAP.

A similar approach as for the primary endpoint will be done for all other continuous efficacy endpoints.

For categorical efficacy endpoints involving proportions of PGA (e.g. the proportion of subjects achieving at least a 2-grade reduction from baseline to clear (0) or almost clear (1) in PGA at week 16), a Cochran Mantel Hansel test (CMH) controlling for PGA at baseline will be performed.

Overall type I error control

For the primary endpoint of percent change-from-baseline in hand mTLSS at Week 16, a Holm's step-down procedure (1979)¹⁴ adjustment will be done to test the two comparisons of interest (40mg vs. Placebo and 80mg vs. Placebo).

9.3.3 Safety Analyses

All safety data, including AEs and SAEs will be presented and tabulated according to MedDRA classification. Descriptions of AEs will include the start date, the stop date (if it resolved), the severity and seriousness of the AE, the causality of the AE to study product, and the outcome. The focus in this protocol will be the prevalence of treatment-emergent adverse events (TEAEs).

Reported AEs will be summarized by the number of subjects reporting the events, as well as by System Organ Class, Preferred Term, severity, seriousness, and relationship to study product. For the summary of AEs by severity, each subject will be counted only once within a System Organ Class or a Preferred Term by using the AEs with the highest intensity within each category for each analysis. For the summary of AEs by relationship to study product, each subject will be counted only once within a System Organ Class or a Preferred Term by using the AEs with the greatest reported relationship within each category. For the summary of AEs by relationship to study product and severity, each subject will be counted only once within a System Organ Class or a Preferred Term by using (1) the greatest reported relationship followed by (2) the highest reported intensity.

All information pertaining to AEs noted during the study will be listed by subject, detailing verbatim, System Organ Class, Preferred Term, start date, stop date, intensity, outcome, and relationship to study product. The AE onset will also be shown relative (in number of days) to the day of study product administration. Serious adverse events will be tabulated by treatment group, relationship to the test article, and a reference to the occurrence of the SAEs to the relative day of dosing.

Results from laboratory analyses, vital signs, and ECGs will be tabulated by treatment and visit using descriptive statistics. The value at each visit as well as the change from baseline will be presented descriptively.

Concomitant medications will be coded with the World Health Organization Drug Dictionary (WHO-DD) and listed by subject. Summary of medication classes will also be tabulated.

No inferential statistics will be done on safety variables.

9.3.4 Pharmacokinetic Analyses

ASN002 concentration data will be listed per subject and summarized descriptively per dose.

Individual plasma concentration vs. actual time profiles for each subject and treatment, as well as the mean (\pm SD) plasma concentration vs. scheduled time profiles for each dose level, will be presented graphically.

9.3.5 Pharmacodynamic Analyses

A biomarker analysis will be performed on blood, tape stripping skin samples and biopsy samples collected to evaluate PD effects of ASN002 on inflammatory markers and cell populations. Biomarker levels will be compared to placebo adjusted change from baseline over time for each treatment group, and the parameters will be summarized by treatment group and overall using descriptive statistics.

9.3.6 Other Analyses

Descriptive summaries of baseline characteristics, including demographic data, prior concomitant therapy, and of subject disposition will be presented. In addition, a list of subjects who discontinued from the study will be provided

Protocol deviations will be summarized by treatment and category.

9.3.7 Planned Interim Analyses

No interim analysis is planned in this study. However, a primary efficacy analysis of the results up to Week 16 visit will be performed after a database lock of all efficacy data of Part A and the sponsor will have access to these unblinded results before the study is completed (Week 32). Safety data up to Week 16 will be cleaned and monitored prior to unblinding the sponsor. Analysis and reporting of the efficacy and safety data will be detailed in the SAP.

The analysis of the results comprised of Week 16 visit up to Week 32 visit will be considered as supportive for the secondary and exploratory objectives of the study.

10 REGULATORY, ETHICAL, AND STUDY OVERSIGHT CONSIDERATIONS

10.1 Local Regulations/Declaration of Helsinki

This study will be conducted in accordance with the ethical principles that have their origin in the Declaration of Helsinki and that are consistent with ICH Tripartite Guideline for GCP and the applicable laws and regulations of the country in which the research is conducted, whichever affords the greater protection to the individual.

10.2 Ethical Review

It is the understanding of the sponsor that this protocol (and any amendments) as well as appropriate consent procedures, will be reviewed and approved by a research ethics board (REB)/institutional review board (IRB). This board must operate in accordance with the current federal regulations. For sites with a local ethics committee, a letter or certification of approval will be sent by the investigator to the sponsor (or CRO) before initiation of the study and also whenever subsequent modifications to the protocol are made.

10.3 Informed Consent Process

An Informed Consent Form describing in detail the study treatment, study procedures, and risks will be given to the subject, along with an assent form when required.

It is the responsibility of the investigator, or a person designated by the investigator (if acceptable by local regulation), to obtain written informed consent from each individual participating in this study, after adequate explanation of the aims, methods, objectives, and potential hazards of the study.

Informed consent is a process that is initiated prior to the individual's agreeing to participate in the study and continues throughout the individual's study participation. Consent forms will be IRB approved, and the subject will be asked to read and review the document. The investigator will explain the research study to the subject and answer any questions that may arise. A verbal explanation will be provided in terms suited to the subject's comprehension of the purposes, procedures, and potential risks of the study and of his or her rights as a research subject. Subjects will have the opportunity to carefully review the written consent form and ask questions prior to signing. The subjects should have the opportunity to discuss the study with their family or surrogates or think about it prior to agreeing to participate.

The subject will sign the informed consent document prior to any procedures being done specifically for the study. Subjects must be informed that participation is voluntary and that they may withdraw from the study at any time for any reason, without prejudice. A copy of the signed informed consent document will be given to the subjects for their records. The informed consent process will be conducted and documented in the source document (including the date), and the form signed, before the subject undergoes any study-specific procedures.

The rights and welfare of the subjects will be protected by emphasizing to them that the quality of their medical care will not be adversely affected if they decline to participate in this study.

If new safety information results in significant changes in the risk/benefit assessment, or if any new information becomes available that may affect the willingness of a subject to continue to participate, the consent form should, if necessary, be reviewed and updated by the REB/IRB. All subjects (including those already being treated) should be informed of the new information, given a copy of the revised form, and asked to give their consent to continue in the study.

10.4 Study Discontinuation and Closure

This study may be temporarily suspended or prematurely terminated if there is sufficient reasonable cause. Written notification, documenting the reason for study suspension or termination, will be provided by the suspending or terminating party to study subjects, investigators, the sponsor, and regulatory authorities. If the study is prematurely terminated or suspended, the principal investigators will promptly inform study subjects and the IRB, and will provide the reason(s) for the termination or suspension. Study subjects will be contacted, as applicable, and be informed of changes to study visit schedule.

Circumstances that may warrant termination or suspension of the study include, but are not limited to the following:

- Determination of unexpected, significant, or unacceptable risk to subjects
- Insufficient compliance to protocol requirements
- Data that are not sufficiently complete or evaluable
- Scientific or corporate reasons

The study may resume once concerns about safety, protocol compliance, and data quality are addressed and satisfy the sponsor, IRB, Health Canada, and FDA.

10.5 Confidentiality and Privacy

Subject confidentiality and privacy are strictly held in trust by the participating investigators, their staff, and the sponsor and their interventions. This confidentiality is extended to cover testing of biological samples in addition to the clinical information relating to subjects. Therefore, the study protocol, documentation, data, and all other information generated will be held in strict confidence.

The investigator must assure that the subjects' anonymity will be maintained and that subjects' identities are protected from unauthorized parties. On case report forms or other documents submitted to the sponsor, subjects should not be identified by their names, but by an identification code. The investigator should keep a subject enrollment log relating codes with the names of subjects. The investigator should maintain in strict confidence documents not for submission to the sponsor (e.g., subjects' written consent forms).

All research activities will be conducted in a setting as private as possible.

The study monitor, other authorized representatives of the sponsor, and representatives of the IRB, regulatory agencies, or pharmaceutical company supplying study product may inspect all documents and records required to be maintained by the investigator, including but not limited to, medical records (office, clinic, or hospital) and pharmacy records for the subjects in this study. The clinical study site will permit access to such records.

The study subject's contact information will be securely stored at each clinical site for internal use during the study. At the end of the study, all records will continue to be kept in a secure location for as long a period as dictated by the applicable legal or regulatory requirements, the reviewing IRB, institutional policies, or sponsor requirements.

Skin and blood samples collected during this study will be stored in a secure storage space with adequate measures to protect confidentiality. Samples will be stored for up to, but no longer than, 15 years from the end of the main study after which time the samples will be destroyed. The samples will be given a code and neither Asana BioSciences LLC. nor its partners will know the subject's identity. The samples will not be sold to other people or companies. The samples may be used when developing new tests, procedures and commercial products.

10.6 Clinical Monitoring

Clinical site monitoring will be conducted to ensure that the rights and well-being of trial subjects are protected; that the reported trial data are accurate, complete, and verifiable; and that the conduct of the trial is in compliance with the currently approved protocol/amendment(s), ICH GCP guidelines, and with applicable regulatory requirement(s). Details of clinical site monitoring will be documented in a Monitoring Plan.

10.7 Quality Assurance and Quality Control

Each clinical site will perform internal quality management of study conduct, data and biological specimen collection, documentation, and completion.

Quality control (QC) procedures will be implemented beginning with the data entry system, and data QC checks, which will be run on the database, will be generated. Any missing data or data anomalies will be communicated to the site(s) for clarification/resolution.

During the study, the sponsor or its representative will conduct monitoring visits at regular intervals. The monitoring visits will be conducted to ensure protocol adherence, quality of data, accuracy of entries on the eCRFs, study product accountability, compliance with regulatory requirements, and continued adequacy of the study site and its facilities.

The site may be audited, monitored, or inspected by a quality assurance officer named by the sponsor, by the REB or IRB, and/or by the regulatory authorities. The investigator will be given notice before an audit occurs and will be expected to cooperate with any audit and provide assistance and documentation (including source data) as requested. The study site will provide direct access to all trial-related sites, source data/documents, and reports for the purpose of monitoring and auditing by the sponsor and inspection by local and regulatory authorities.

10.8 Data Handling and Record Keeping

Data collection is the responsibility of the clinical trial staff at the site under the supervision of the site investigator. The investigator is responsible for ensuring the accuracy, completeness, legibility, and timeliness of the data reported.

The investigator must maintain adequate and accurate records to enable the conduct of the study to be fully documented and the study data to be subsequently verified. These documents should be classified into two separate categories: investigator's study files and subject clinical source documents.

The investigator must maintain source documents for each subject in the study. These source documents will consist of case and visit notes (clinical medical records) containing demographic and medical information and the results of any tests or assessments. All information on the eCRFs must be traceable to the source documents in the subject's file. Data not requiring a written or electronic record will be defined before study start and will be recorded directly on the eCRFs, which will be documented as being the source data.

The records should be retained by the investigator according to ICH guidelines, local regulations, or as specified in the Clinical Trial Agreement, whichever retention period is longer.

Subject data will be entered by site personnel using [REDACTED], a web-based electronic data capture (EDC) and reporting system. This application will be set up for remote entry. [REDACTED] is the developer and owner of [REDACTED]. The EDC software has been fully validated and conforms to Title 21 of the Code of Federal Regulations, Part 11 requirements. Investigator site staff will not be given access to the EDC system until they have been fully trained. Designated investigator staff will enter the data required by the protocol into the eCRFs using this web-based application. Automatic validation programs check for data discrepancies in the eCRFs and, by generating appropriate error messages, allow modification or verification of the entered data by the investigator staff before confirming the data. The investigator must certify that the data are complete and accurate by applying an electronic signature to the eCRFs.

The data collected will be encoded and stored electronically in a database system. Validated data may subsequently be transferred to the sponsor.

10.9 Protocol Deviations

A protocol deviation is any noncompliance with the clinical trial protocol requirements. The noncompliance may be either on the part of the subject, the investigator, or the study site staff. As a result of deviations, corrective actions are to be developed by the site and implemented promptly.

Protocol deviations must be sent to the reviewing IRB/EC per their policies. The investigator is responsible for knowing and adhering to the reviewing IRB/EC requirements.

10.10 Publication Policy

The publication policy will be addressed in the Research and Financial Agreement, and all details

outlined in the agreement will apply to this protocol. The trial will be registered on ClinicalTrials.Gov prior to the first subject being dosed.

APPENDIX A: Work Productivity and Activity Impairment Questionnaire (WPAI-SHP:CHE)

Subject ID #: _____	-	Subject Initials: _____
Visit: _____	Visit Date (dd-mmm-yyyy): _____	
Section to be completed by site staff		

Work Productivity and Activity Impairment Questionnaire: Specific Health Problem V2.0 (WPAI:SHP:CHE)

The following questions ask about the effect of your *CHRONIC HAND ECZEMA* on your ability to work and perform regular activities. *Please fill in the blanks or circle a number, as indicated.*

1. Are you currently employed (working for pay)? _____ NO _____ YES
If NO, check “NO” and skip to question 6.

The next questions are about the **past seven days**, not including today.

2. During the past seven days, how many hours did you miss from work because of problems associated with your CHRONIC HAND ECZEMA? *Include hours you missed on sick days, times you went in late, left early, etc., because of your CHRONIC HAND ECZEMA. Do not include time you missed to participate in this study.*

_____ HOURS

3. During the past seven days, how many hours did you miss from work because of any other reason, such as vacation, holidays, time off to participate in this study?

_____ HOURS

[figure not shown]
4. During the past seven days, how many hours did you actually work?

_____ HOURS *(If “0”, skip to question 6.)*

5. During the past seven days, how much did your CHRONIC HAND ECZEMA affect your productivity while you were working?

Think about days you were limited in the amount or kind of work you could do, days you accomplished less than you would like, or days you could not do your work as carefully as usual. If CHRONIC HAND ECZEMA affected your work only a little, choose a low number. Choose a high number if CHRONIC HAND ECZEMA affected your work a great deal.

Consider only how much CHRONIC HAND ECZEMA affected productivity while you were working.

[figure not shown]

CIRCLE A NUMBER

6. During the past seven days, how much did your CHRONIC HAND ECZEMA affect your ability to do your regular daily activities, other than work at a job?

By regular activities, we mean the usual activities you do, such as work around the house, shopping, childcare, exercising, studying, etc. Think about times you were limited in the amount or kind of activities you could do and times you accomplished less than you would like. If CHRONIC HAND ECZEMA affected your activities only a little, choose a low number. Choose a high number if CHRONIC HAND ECZEMA affected your activities a great deal.

Consider only how much CHRONIC HAND ECZEMA affected your ability to do your regular daily activities, other than work at a job.

CIRCLE A NUMBER

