13.3 Exploratory Endpoints

Chronic Eczema Subtype Analysis

Subgroup analysis using descriptive statistics by baseline description of CHE (hyperkeratotic, fingertip or pompholyx) will be performed using the primary endpoint - percent change in mTLSS.

Subgroup analysis using descriptive statistics by baseline description of CHE will also be performed for the PGA response outcome as defined in Section 13.2.

Pruritus NRS section of hand mTLSS

PPD	STATISTICAL ANALYSIS PLAN, Version Final 1.0
Protocol Number: ASN002AD-202 V6.0	Sponsor: Asana BioSciences, LLC

The pruritus/pain parameter score of the hand mTLSS questionnaire will be analyzed using descriptive statistics.

Work Productivity and Activity Impairment Measure: Specific Health Problem

The work productivity and activity impairment: specific health problem (WPAI:SHP) measure will be assessed at the visits specified in [Table 1](#), and evaluated for CHE. It is a simple 6-question validated questionnaire that has been used for different health conditions and customized by replacing the word PROBLEM of the questionnaire by the condition that is studied. Its use has been described in many publications, including many multinational studies.

The WPAI-SHP allows us to calculate four scores (multiply by 100 for percent):

Percent work time missed due to CHE: $Q2/(Q2+Q4)$

Percent impairment while working due to CHE: $Q5/10$

Percent overall work impairment due to CHE: $Q2/(Q2+Q3) + \{(1-(Q2)/(Q2+Q3)) \times Q5/10\}$

Percent activity impairment due to CHE: $Q6/10$

Where variables Q1-Q6 are the questions from WPAI-SHP:

Questions:

- 1 = currently employed
- 2 = hours missed due to CHE
- 3 = hours missed other reasons
- 4 = hours actually worked
- 5 = degree CHE affected productivity while working
- 6 = degree CHE affected regular activities

WPAI-SHP scores will be analyzed as follows:

- Change from baseline in Work Productivity and Activity Impairment – Specific Health Problem (WPAI-SHP) questionnaire at all visits with assessments scheduled from Weeks 4 to Week 32 for each domain
- Proportion of patients with 20% or higher impairment in Work Productivity and Activity Impairment – Specific Health Problem (WPAI-SHP) questionnaire at all visits with assessments scheduled from Weeks 4 to Week 32 for each domain

PPD	STATISTICAL ANALYSIS PLAN, Version Final 1.0
Protocol Number: ASN002AD-202 V6.0	Sponsor: Asana BioSciences, LLC

Extent of Disease

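### SAP 13.3 has no rule for WPAI overall work impairment when an employed subject worked no hours: read literally, the score is missing while the SAP's own work-time-missed score is 100%

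*Protocol*

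**What the plan says.** Protocol Appendix A collects four work items from employed subjects, all for the past seven days:

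- Q2: "how many hours did you miss from work because of problems associated with your CHRONIC HAND ECZEMA"
- Q3: "how many hours did you miss from work because of any other reason"
- Q4: "During the past seven days, how many hours did you actually work"
- Q5, scored 0 to 10: "how much did your CHRONIC HAND ECZEMA affect your productivity while you were working"

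A subject who enters zero at Q4 is told to "skip to question 6", so Q5 is then blank by design.

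SAP 13.3 derives four scores. "Percent work time missed due to CHE" is Q2/(Q2+Q4), with "4 = hours actually worked". Impairment while working is Q5/10. "Percent overall work impairment due to CHE" is Q2/(Q2+Q3) + {(1 − Q2/(Q2+Q3)) × Q5/10}. Activity impairment is Q6/10. Each score is reported as change from baseline and as the proportion with 20% or higher impairment, at scheduled visits from Week 4 to Week 32.

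The SAP has missing-item rules for mTLSS (13.1) and for HECSI and DLQI (13.2). It has none for the WPAI. WPAI results are summarized descriptively (13.3), and the software is SAS 9.4 or higher (5.8).

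**The concern.** The form and the formula do not fit together. One omits Q5 when no hours were worked; the other needs Q5 every time. Being off work for a whole week is foreseeable here: Protocol 2.1.1 describes prolonged sick leave in severe CHE and cites a survey in which 21% of patients had been on sick leave at least once because of hand eczema, and Protocol 4.1 caps moderate disease at 30% of enrollment.

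Because Q5 is skipped only when no hours were worked, missingness in this score depends on the outcome being measured. A subject in this state at baseline has no change from baseline at any visit; one who enters it later loses that visit. The 20% flag is also exposed. A plain SAS comparison treats a missing value as below 20, and SAP Appendix 1 by default takes percentages over all subjects in the population. A wholly absent worker could therefore count as not impaired.

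**Working it through.** The plan states no figure to reproduce; this is a check of the scoring rule. In SAS arithmetic a missing operand gives a missing result, including 0 × missing, and so does division by zero. The hours below are examples.

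**Whole week lost to CHE.** Q2 = 40, Q3 = 0, Q4 = 0, Q5 blank.

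- Work time missed: 40/(40+0) = 100%.
- Overall, as printed: 40/40 + (1 − 40/40) × Q5/10 = 1 + 0 × missing = missing.
- Weeks of 8 h and 60 h give the same pair of results.
- Q5 has weight 1 − 1 = 0, so the expression equals 100% for every Q5 from 0 to 10. The value is determined; only the instruction is absent.

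**No hours worked, part of the absence for other reasons.** Work time missed is Q2/(Q2+0) = 100% in each row, but the printed overall formula gives Q5 a non-zero weight:

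| Q2 | Q3 | Printed overall formula | Range over Q5 = 0 to 10 |
|---|---|---|---|
| 32 | 8 | 0.80 + 0.20 × Q5/10 | 80% to 100% |
| 20 | 20 | 0.50 + 0.50 × Q5/10 | 50% to 100% |
| 1 | 39 | 0.025 + 0.975 × Q5/10 | 2.5% to 100% |

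So 100% follows for every case with Q4 = 0 and Q2 > 0 only if the overall formula uses Q2/(Q2+Q4).

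**The Q3 denominator affects other workers too.**

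- Q2 = 0, Q3 = 0, Q4 = 40, Q5 = 5: the printed formula gives 0/0 = missing; with Q4 it gives 0 + 1 × 0.5 = 50%.
- Q2 = 20, Q3 = 0, Q4 = 20, Q5 = 0: the printed formula gives 100%; with Q4 it gives 50%.

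**Does correcting the denominator suffice?** No. With Q2 = 40 and Q4 = 0 it gives 1 + 0 × missing = missing. With the added rule the result is 100%, also for the 32 + 8 and 20 + 20 cases. Holiday only (Q2 = 0, Q3 = 40, Q4 = 0) stays missing, as it should.

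**Possible size, by assumption.** Suppose the denominator is corrected, a share s of employed subjects is wholly absent (score 100%), and the rest average m. The mean at a visit is then 100s + m(1 − s) with the rule and m without it, a shift of s(100 − m):

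| s | m = 20% | m = 40% |
|---|---|---|
| 2% | 21.6 against 20 (1.6 points) | 41.2 against 40 (1.2) |
| 5% | 24 against 20 (4.0) | 43 against 40 (3.0) |
| 10% | 28 against 20 (8.0) | 46 against 40 (6.0) |

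Neither s nor m is in the documents.

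**The case against.** The SAP never says that a skipped Q5 makes the score missing. A careful programmer could special-case Q4 = 0, and the instrument's usual scoring conventions may cover it in a cited source that cannot be checked here. That is fair as far as it goes: what is shown is a missing instruction whose literal execution loses the score. The questionnaire itself is not at fault.

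A reader might also infer several stronger things that the documents do not support:

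- *Only the worst-affected workers are lost, so burden is understated.* As printed, workers with no absence at all (Q2 = Q3 = 0) are lost too, and some partial absences are scored 100%. The net direction cannot be stated.
- *A return to work never registers.* Work time missed does not use Q5 and would record the fall from 100%. Activity impairment is also kept.
- *The benefit of ASN002 is understated.* New absence on active drug would vanish just as new absence on placebo would, and no between-arm test of the WPAI is planned.
- *A specific loss of improvement can be quoted.* If 2 of 28 employed subjects in an arm went from 100% to 35% and the other 26 improved by d points, the lost mean improvement would be 2(65 − d)/28: 4.6 at d = 0, 3.9 at d = 10, 3.2 at d = 20. Every input is invented.

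**Conclusion.** The point holds as a scoring gap in SAP 13.3. For an employed subject with Q4 = 0 and Q2 > 0, the overall work impairment formula taken literally returns missing, while the SAP's other absence score for the same week is 100%. One of the four WPAI scores loses a value it should have. Impairment while working is rightly not applicable in that week, and the remaining two scores are intact. The 100% value rests on aligning the overall formula's time-missed fraction with Q2/(Q2+Q4); under the printed fraction it is fixed only when Q3 = 0. The number of subjects affected cannot be derived from the documents, nor can the direction of any effect on the comparison between arms. Severity is minor because the endpoint is exploratory and descriptive.

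**What to change.** In SAP 13.3, make two changes together:

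1. Write overall work impairment as Q2/(Q2+Q4) + {(1 − Q2/(Q2+Q4)) × Q5/10}, with the same time-missed fraction as the first score.
2. Add: *If Q4 = 0 and Q2 > 0, overall work impairment is 100% and impairment while working is missing. If Q2 = 0 and Q4 = 0, all three work scores are missing.*

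Use the resulting score in both the change from baseline and the 20% proportion, and leave the 20% flag blank where the score is missing. The cost is a corrected formula, one scoring rule and one line of code, using data already collected. Settling it before the Part A lock avoids a scoring decision made after unblinding.
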